8.1.3 Assessment of Adverse Events by the Investigator

The Investigator will assess the severity (intensity) of each AE, and will also categorize each AE as to its potential relationship to study drugs using the categories of yes or no.

Assessment of severity

The severity of all AEs should be graded according to the NCI CTCAE v5.0. For those AE terms not listed in the NCI CTCAE, the following grading system should be used:

- NCI CTCAE Grade 1: Mild; asymptomatic or mild symptoms; clinical or diagnostic observations only; intervention not indicated;
- NCI CTCAE Grade 2: Moderate; minimal local or non-invasive intervention indicated; limiting age-appropriate instrumental activities of daily living;
- NCI CTCAE Grade 3: Severe or medically significant but not immediately life-threatening; hospitalization or prolongation of hospitalization indicated; disabling; limiting self-care activities of daily living;
- NCI CTCAE Grade 4: Life-threatening consequences; urgent intervention indicated; and
- NCI CTCAE Grade 5: Death related to the AE.

Causality assessment

The relationship of an AE to the administration of the study drugs is to be assessed according to the following definitions:

- No (unrelated, not related, unlikely to be related) The time course between the administration of study drugs and the occurrence or worsening of the AE rules out a causal relationship and another cause (concomitant drugs, therapies, complications, etc) is suspected.
- Yes (possibly, probably, or definitely related) The time course between the administration of study drugs and the occurrence or worsening of the AE is consistent with a causal relationship and no other cause (concomitant drugs, therapies, complications, etc) can be identified.

The definition implies a reasonable possibility of a causal relationship between the event and the study drugs. This means that there are facts (evidence) or arguments to suggest a causal relationship.

The following factors should also be considered:

- The temporal sequence from study drugs administration-
 - The event should occur after the study drugs are given. The length of time from study drugs' exposure to event should be evaluated in the clinical context of the event.
- Underlying, concomitant, intercurrent diseases-
 - Each report should be evaluated in the context of the natural history and course of the disease being treated and any other disease the patient may have.
- Concomitant drug-
 - The other drugs the patient is taking or the treatment the patient receives should be examined to determine whether any of them might be recognized to cause the event in question.
- Known response pattern for this class of study drugs-
 - Clinical and/or preclinical data may indicate whether a particular response is likely to be a class effect.
- Exposure to physical and/or mental stresses-
 - The exposure to stress might induce adverse changes in the recipient and provide a logical and better explanation for the event.
- The pharmacology and pharmacokinetics of the study drugs-
 - The known pharmacologic properties (absorption, distribution, metabolism, and excretion) of the study drugs should be considered.

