3.1.1.1 Dose-limiting toxicities

All toxicities will be graded using National Cancer Institute (NCI) Common Terminology Criteria for Adverse Events (CTCAE) v5.0 based on the Investigator assessment.

The DLT window of observation will be during Cycle 1 (initial 6 weeks of study treatment).

The occurrence of any of the following toxicities during Cycle 1 will be considered a DLT, if assessed by the Investigator to be possibly, probably, or definitely related to study treatment administration:

- 1. Grade 4 non-hematologic toxicity (not laboratory);
- 2. Grade 4 hematologic toxicity lasting ≥7 days, except thrombocytopenia:
 - o Grade 4 thrombocytopenia of any duration; or
 - o Grade 3 thrombocytopenia associated with clinically significant bleeding.
- 3. Any non-hematologic AE ≥Grade 3 in severity should be considered a DLT, with the following exceptions:
 - o Grade 3 fatigue lasting ≤3 days;
 - o Grade 3 diarrhea, nausea, or vomiting unless it persists for >3 days despite the use of anti-emetics or anti-diarrheals per standard of care; or
 - o Grade 3 rash without use of corticosteroids or anti-inflammatory agents per standard of care.
- 4. Any Grade 3 or Grade 4 non-hematologic laboratory value if:
 - o Clinically significant medical intervention is required to treat the patient;
 - o The abnormality leads to hospitalization;
 - o The abnormality persists for >1 week; or

- The abnormality results in a drug-induced liver injury.
- Exceptions: Clinically non-significant, treatable, or reversible laboratory abnormalities including liver function tests, uric acid, etc. Isolated laboratory abnormalities ≥Grade 3 (not present at baseline) that resolve to <Grade 1 in <3 days without clinical sequelae or need for therapeutic intervention.

- 5. Febrile neutropenia Grade 3 or Grade 4:
 - o Grade 3 is defined as absolute neutrophil count (ANC) <1000/mm³ with a single temperature of >38.3°C (101°F) or a sustained temperature of ≥38°C (100.4°F) for more than 1 hour; or
 - o Grade 4 is defined as ANC <1000/mm³ with a single temperature of >38.3°C (101°F) or a sustained temperature of ≥38°C (100.4°F) for more than 1 hour with life-threatening consequences and urgent intervention indicated.
- 6. Prolonged delay (>2 weeks) in initiating Cycle 2 due to treatment-related toxicity;
- 7. Delay in administration of CyPep-1 for >7 days;

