When study interventions are administered in combination, attribution of an AE to a single component is likely to be difficult. Therefore, while the Investigator may attribute a toxicity event to the combination, to CyPep-1 alone, or to pembrolizumab alone, for AEs listed in Table 10, both interventions must be held according to the criteria in Table 10.

Holding study interventions

When study interventions are administered in combination, if the AE is considered immune-related, both interventions should be held according to recommended dose modifications.

[figure not shown]
Restarting study interventions

Patients may not have any dose modifications (no change in dose or schedule) of pembrolizumab in this study, as described in Table 10.

[figure not shown]
If the toxicity does not resolve or the criteria for resuming treatment are not met, the patient must be discontinued from all study interventions.

If the toxicities do resolve and conditions are aligned with what is defined in Table 10, the combination of CyPep-1 and pembrolizumab may be restarted at the discretion of the Investigator. In these cases where the toxicity is attributed to the combination or to CyPep-1 alone, re-initiation of pembrolizumab as a monotherapy may be considered after communication with, and agreement by, the Sponsor.

administered at a Q2W schedule as described in the Schedule of Assessments (Appendix A).

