8.1.1 Adverse (Drug) Reaction

All noxious and unintended responses to a medicinal product related to any dose should be considered an adverse drug reaction. "Responses" to a medicinal product means that a causal relationship between a medicinal product and an AE is at least a reasonable possibility, ie, the relationship cannot be ruled out.

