3.7.1 Adverse Events (AEs)

AEs will be captured from the date of informed consent through study completion. All AEs will be coded to system organ class and preferred term using MedDRA version 25.0. Treatment-emergent adverse events (TEAEs) are defined as AEs that start or worsen after the first dose of study drug and within 30 days after the last dose of study treatment.

Adverse events of clinical interest (AECI) include the following:

- An overdose of pembrolizumab, as defined in Section 5.5.3.4 of the protocol; and
- An elevated aspartate aminotransferase (AST) or alanine aminotransferase (ALT) laboratory value that is greater than or equal to 3 times the upper limit of normal (ULN) (greater than 5 times the ULN for patients with liver metastases), an elevated total bilirubin laboratory value that is greater than or equal to twice the ULN, and, at the same time, an alkaline phosphatase laboratory value that is less than twice the ULN, as determined by way of protocol-specified laboratory testing or unscheduled laboratory testing.

An overview of TEAEs will be provided including counts and percentages of patients (and event counts) with the following:

- TEAEs;
- CyPep-1 related TEAEs (overall and by maximum severity);
- TEAEs related to any Investigational Medicinal Product (IMP) (CyPep-1 or pembrolizumab);
- CTCAE Grade 3/4/5 TEAEs;
- Treatment-emergent serious AEs (TESAEs);
- CyPep-1 related TESAEs;
- TESAEs related to any IMP (CyPep-1 or pembrolizumab);
- Serious adverse events (SAEs);
- TEAEs leading to interruption of CyPep-1;
- TEAEs leading to interruption of pembrolizumab;
- TEAEs leading to delayed or held CyPep-1 dose;
- TEAEs leading to delayed or held pembrolizumab;
- TEAEs leading to permanent discontinuation of CyPep-1;
- TEAEs leading to discontinuation of pembrolizumab;
- TEAEs leading to discontinuation of study;
- · TEAEs leading to death; and
- TEAEs of clinical interest.

Counts and percentages of patients (and event counts) will also be presented by system organ class (SOC) and preferred term (PT) for each of the categories in the overview. For these summaries, patients with multiple adverse events will be counted only once per SOC or PT.

A by-patient adverse event data listing will be presented including, but not limited to, verbatim term, preferred term, SOC, CTCAE grade, and relationship to any study drug. SAEs, and AEs leading to discontinuation of study drug, AEs leading to death, and AECIs will also be listed.

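### The two causality categories in Protocol 8.1.3 are not complementary, so an event with compatible timing and a plausible alternative cause fits neither, and whether it counts as a DLT or related TEAE depends on who classifies it

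*Protocol*

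**What the plan says.** Protocol 8.1.3 tells the investigator to "categorize each AE as to its potential relationship to study drugs using the categories of yes or no".

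- *Yes* is labelled as covering possibly, probably and definitely related events. It applies when the interval from dosing to the occurrence or "worsening of the AE is consistent with a causal relationship and no other cause (concomitant drugs, therapies, complications, etc) can be identified".
- *No* is labelled as covering unrelated, not related and unlikely related events. It applies when that interval to the occurrence or "worsening of the AE rules out a causal relationship and another cause (concomitant drugs, therapies, complications, etc) is suspected".

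The same section then says that the definition implies a reasonable possibility of causation, and adds: "This means that there are facts (evidence) or arguments to suggest a causal relationship". Protocol 8.1.1 defines an adverse drug reaction by a causal relationship that is "at least a reasonable possibility, ie, the relationship cannot be ruled out".

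Relatedness is then used in two places. Under Protocol 3.1.1.1, the listed toxicities count as DLTs only "if assessed by the Investigator to be possibly, probably, or definitely related to study treatment administration". SAP 3.7.1 tabulates TEAEs and serious TEAEs related to CyPep-1, and separately those related to either study drug. SAP 3.1.6 leaves missing values missing unless a rule says otherwise, and no rule is given for a missing relationship.

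**The concern.** A binary scale needs two definitions that between them cover every event. Here each definition joins two conditions with *and*, and neither is the negation of the other, so some events satisfy neither. The combination of compatible timing with a plausible other cause can readily arise in this population. All patients have advanced cancer, and Arms A and B, with the checkpoint-eligible part of Arm C, have already received a checkpoint inhibitor.

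The *Yes* definition also contradicts text around it. Its label includes possibly related events, yet any identifiable alternative cause disqualifies an event. The reasonable-possibility sentence and the standard in 8.1.1 are both more inclusive. On the other side, events unlikely to be related are placed under *No*, although *No* requires timing to exclude causation altogether.

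Two investigators can therefore classify the same event differently, and each can cite the protocol. One who applies *Yes* literally would not call such an event related, so it could be neither a DLT nor a related TEAE. DLT incidence is one of three Phase 1b primary endpoints, and it is the one that drives the dose-confirmation rule in Protocol 3.1.1.

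**Working it through.** **Step 1. Do the definitions cover all cases?** Inputs: the two definitions in Protocol 8.1.3. Cross timing with the presence of another cause.

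| Timing | Another cause | Meets *Yes*? | Meets *No*? | Result |
|---|---|---|---|---|
| Compatible | None identified | Yes | No | Related |
| Compatible | Present | No | No | Neither |
| Excludes causation | Present | No | Yes | Not related |
| Excludes causation | None identified | No | No | Neither |

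Two of the four combinations have no category. The second row is the one that matters for safety counts.

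**Step 2. Apply each standard in the protocol to the second row.**

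- The *Yes* definition in 8.1.3: not related, because another cause is identifiable.
- The *No* definition in 8.1.3: cannot be called not related, because timing does not exclude causation.
- The reasonable-possibility sentence in 8.1.3: related, if facts or arguments suggest causation.
- Section 8.1.1: related, if the relationship cannot be excluded.

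DLT criterion 8 in 3.1.1.1 (the liver-test criterion) carries its own explicit exclusion for progression or other illness. Read literally, the *Yes* definition extends an other-cause exclusion to every criterion.

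**Step 3. Illustration of what is at stake.** The plan states no figure on this point, so there is none to reproduce. Inputs: six patients, with more than 2 DLTs leading to de-escalation (Protocol 3.1.1). The true DLT rate *p* and the share *m* of true DLTs not called related are both assumed; the documents give neither. With *q* = *p*(1 − *m*),

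P(X ≤ 2) = (1 − *q*)^6 + 6*q*(1 − *q*)^5 + 15*q*²(1 − *q*)^4.

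| Assumed *p* | *m* = 0 | *m* = 25% | *m* = 50% |
|---|---|---|---|
| 0.20 | *q* = 0.20: 0.901 | *q* = 0.15: 0.953 | *q* = 0.10: 0.984 |
| 0.40 | *q* = 0.40: 0.544 | *q* = 0.30: 0.744 | *q* = 0.20: 0.901 |

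Example at *q* = 0.30: 0.118 + 0.303 + 0.324, which gives 0.744 from unrounded terms.

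With complementary categories all four rows of the first table are classified and *m* from this source is zero, which is the first column.

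**The case against.** The best defence is that the section should be read whole. The reasonable-possibility sentence follows the definitions directly, and the list after it treats underlying disease and other drugs as factors to weigh, not as automatic exclusions. An investigator guided by that text would reach the standard of 8.1.1. There is also a safety net. All TEAEs, Grade 3/4/5 TEAEs and serious events are tabulated regardless of relationship (SAP 3.7.1), serious events in the reporting window are reported within 24 hours whatever the cause (Protocol 8.3), and the DMC and sponsor review the safety data as a whole. This limits the harm, but it does not repair the definitions: the softer sentences contradict the two category definitions and do not amend them.

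A reader might infer four stronger things that the documents do not support.

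- *That each study drug is another cause for its partner, so DLTs are lost that way.* Protocol 5.6.4 defines concomitant medication as what is used in addition to CyPep-1 and pembrolizumab, and the DLT rule refers to study treatment. The two-drug difficulty concerns the CyPep-1-specific tables, where Protocol 5.5.3.3 concedes that "attribution of an AE to a single component is likely to be difficult".
- *That the bias runs toward confirming the dose.* An ambiguous event fails *No* as clearly as *Yes*, so a forced choice could go either way.
- *That such events are the usual case.* No document gives their share, and exclusion criteria 2 and 15 restrict carry-over toxicity from earlier treatment.
- *That the enrolment-stop criteria are compromised.* Those in Protocol 4.5.3 apply to Phase 2a patients, and SAP section 1 says the study terminated after Phase 1b.

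**Conclusion.** The causality rule is wrong as written, not merely short of detail. Its two categories leave gaps, and the *Yes* definition contradicts its own label, the sentence that follows it and section 8.1.1. That conclusion rests on the text alone and needs no assumption. What follows from it is inconsistent classification of ambiguous events, with the possibility that some are left out of the DLT count and the related TEAE and serious TEAE tables.

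The size of that loss cannot be derived from the documents. The binomial figures depend wholly on two assumed inputs. They show modest sensitivity at a true DLT rate of 0.20 (0.90 rising to at most 0.98) and considerable sensitivity at 0.40 (0.54 rising to 0.90 if half are lost). They are not an estimate of what happened in the six planned patients.

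**What to change.** Reconcile Protocol 8.1.3 with 8.1.1 so that each category is the complement of the other:

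- *Yes*: there is a reasonable possibility of a causal relationship that cannot be excluded, whether or not another cause is also possible.
- *No*: there is no reasonable possibility, either because timing excludes it or because another cause explains the event.

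State that both study drugs may be marked as related to the same event, which the CyPep-1-specific tables need.

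Because the study ended after Phase 1b, rewording the protocol does little for relationship calls already recorded. The SAP should therefore also (a) count a missing relationship as related, and (b) list all Cycle 1 events that meet the DLT severity criteria regardless of the causality call, so that a reader can see which events the DLT count depends on.

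The cost is one paragraph in 8.1.3 and the matching eCRF completion guidance, plus one rule and one listing in the SAP for a planned six patients. The downside is that more events will be classed as related.

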8.1.4 Adverse Events of Clinical Interest

Selected non-serious AEs and SAEs are also known as AECIs and must be reported to the Sponsor within 24 hours of the Investigator's awareness.

AECIs for this study include the following:

- An overdose of pembrolizumab, as defined in Section 5.5.3.4; and
- An elevated AST or ALT laboratory value that is greater than or equal to 3 times the ULN (greater than 5 times the ULN for patients with liver metastases), an elevated total bilirubin laboratory value that is greater than or equal to twice the ULN, and, at the same time, an alkaline phosphatase laboratory value that is less than twice the ULN, as determined by way of protocol-specified laboratory testing or unscheduled laboratory testing.

Note: These criteria are based upon available regulatory guidance documents. The purpose of the criteria is to specify a threshold of abnormal hepatic tests that may require an additional evaluation for an underlying etiology. The study site guidance for assessment and follow-up of these criteria can be made available. It may also be appropriate to conduct additional evaluation for an underlying etiology in the setting of abnormalities of liver blood tests including AST, ALT, bilirubin, and alkaline phosphatase that do not meet the criteria noted above. In these cases, the decision to proceed with additional evaluation will be made through consultation between the study Investigators and the Sponsor Clinical Director. However, abnormalities of liver blood tests that do not meet the criteria noted above are not AECIs for this study.

8.2 Serious Adverse Events

An AE or adverse reaction is considered serious if, in the view of either the Investigator or Sponsor, it results in any of the following outcomes:

Death;

Note: Death due to tumor-related symptoms or tumor progression will not be recorded as an SAE under this criterion.

• A life-threatening AE;

Note: An AE or adverse reaction is considered "life-threatening" if, in view of either the Investigator or Sponsor, its occurrence places the patient at immediate risk of death. It does not include an event that, had it occurred in a more severe form, might have caused death.

• Requires hospitalization or prolongation of existing hospitalizations;

Note: Any hospital admission with at least 1 overnight stay will be considered an inpatient hospitalization. An emergency room or urgent care visit without hospital admission will not be recorded as an SAE under this criterion, nor will hospitalization for a procedure scheduled or planned before signing of informed consent, elective treatment of a pre-existing condition that did not worsen from baseline, or hospitalization due to tumor-related symptoms or tumor progression. However, unexpected complications and/or prolongation of hospitalization that occur during elective surgery should be recorded as AEs and assessed for seriousness. Admission to the hospital for social or situational reasons (ie, no place to stay, live too far away to come for hospital visits, respite care) will not be considered inpatient hospitalizations.

- A persistent or significant disability/incapacity or substantial disruption of the ability to conduct normal life functions;
- A congenital anomaly/birth defect; or
- An important medical event.

Note: Important medical events that do not meet any of the above criteria may be considered an SAE when, based upon appropriate medical judgment, they may jeopardize the patient and may require medical or surgical intervention to prevent one of the outcomes listed above. Examples of such medical events include allergic bronchospasm requiring intensive treatment in an emergency room or at home, blood dyscrasias or convulsions that do not result in inpatient hospitalizations, or the development of drug dependency.

Note: Events of progression of a patient's underlying cancer, as well as events clearly related to the progression of a patient's cancer (signs/symptoms of progression) should not be reported as an SAE; however, when a patient dies from the progression of underlying cancer, the event will be captured as an outcome on an eCRF for death due to disease progression. Diagnosis of progression of disease or hospitalization due to signs and symptoms of disease progression alone should not be reported as an SAE.

8.3 Serious Adverse Event Reporting – Procedures for Investigators

Initial reports

All SAEs occurring from the time of signing the ICF until 90 days (30 days if patients initiate new anti-cancer therapy) after the last dose of study treatment must be reported to Medpace Clinical Safety within 24 hours of the knowledge of the occurrence.

Any SAE brought to the attention of the Investigator at any time outside of the time period specified above must be reported immediately, or within 24 hours of the knowledge of the occurrence, to Medpace Clinical Safety or the Sponsor/designee if the event is considered to be drug-related.

To report the SAE, complete the SAE form electronically in the electronic data capture (EDC) system for the study. When the form is completed, Medpace Safety personnel will be notified electronically by the EDC system and will retrieve the form. If the event meets serious criteria and it is not possible to access the EDC system, send an email to Medpace Safety at [contact] or call the Medpace SAE reporting line (phone number listed below), and fax/email the completed paper SAE form to Medpace (contact information listed in Section 8.6) within 24 hours of awareness. When the EDC system becomes available, the SAE information must be entered within 24 hours of the system becoming available.

Follow-up reports

The Investigator must continue to follow the patient until the SAE has subsided or until the condition becomes chronic in nature, stabilizes (in the case of persistent impairment), or the patient dies.

Within 24 hours of receipt of follow-up information, the Investigator must update the SAE form electronically in the EDC system for the study and submit any supporting documentation (eg, patient discharge summary or autopsy reports) to Medpace Clinical Safety via fax or email. If

it is not possible to access the EDC system, refer to the procedures outlined above for initial reporting of SAEs.

